Study Protocol with Statistical Analysis Plan
SAFE Workplace Intervention for People With IDD

Official Title: Efficacy of the SAFE Program to Promote Preventative Behaviors of Airborne Diseases (COVID-19) and Improve Well-Being for People with Intellectual and Developmental Disabilities in the Workplace

NCT06112249

November 6, 2025

1) Abstract of the study

The purpose of this study is to examine the feasibility and efficacy of a systematic training approach targeting behaviors to increase safety and prevention of airborne diseases such as COVID-19 in the workplace for individuals with Intellectual and Developmental Disabilities (IDD). *This project is designed to determine proof of concept and proof of product for a peer support intervention, the **SAFE** program, to increase knowledge and safe workplace practices.* There is an identified immediate need for individuals with IDD to receive training in an accessible format. The **SAFE program** has been developed in an accessible format for those with IDD. It focuses on education regarding actionable behaviors that reduce the risk of acquiring and transmitting COVID-19 and other airborne diseases. The study will implement a peer-mediated and occupational therapy lead program, **SAFE**, to identify and address potential implementation issues and further refine the program curriculum. Additionally, the efficacy of the program on perceived safety and well-being, observable preventative behaviors and self-advocacy will be examined.

2) Protocol Title

Efficacy of the **SAFE** Program to Promote Preventative Behaviors of Airborne Diseases (COVID-19) and Improve Well-Being for People with Intellectual and Developmental Disabilities in the Workplace

3) Investigator

[name], OTR/L, BCP, FAOTA

[name]

4) Sponsor:

PA Department of Health

5) Objectives

It is hypothesized that the **SAFE program** will have a positive effect on perceived well-being and knowledge of the actionable behaviors for the prevention of COVID-19 and other airborne diseases. The program will have a larger effect on outcomes when provided using peer support compared to staff training. Individuals with IDD will demonstrate increased knowledge and safe behaviors after completing the **SAFE program**. Peer-interventionists will report perceived benefits and limitations of participating in training and providing peer-mediated travel training interventions to identify potential outcomes for future research.

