The research intends to answer these questions:

1. Does participation in the **SAFE program** increase perceived safety and well-being in the workplace for people with ASD and/or IDD?

SAFE Protocol

2. Does participation in the *SAFE program* increase knowledge of actionable behaviors to prevent transmission of airborne diseases (i.e. COVID-19) in the workplace for people with IDD?
3. When implemented through *peer support*, does the *SAFE program* have a larger increase in perceived well-being and knowledge of actionable behaviors to prevent transmission of airborne diseases (i.e. COVID-19) than when implemented through staff training and supports?

The research further intends to:

- Develop health communication messages related to safe interactions and the prevention of COVID-19 and other infectious airborne diseases for autistic adults
- Refine and expand the SAFE program based on stakeholder priorities and input Evaluate the SAFE program training with Autistic adults

Phase 2

1: Identify stakeholder priorities for additional health communication content related to staying safe from infectious airborne diseases.

2: Develop new content based on the identified needs and incorporate it into the SAFE program for individuals with IDD.

3: Pilot the new curriculum with direct care providers and refine materials based on feedback to ensure effectiveness.

6) Rationale and Significance

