We intend to complete the **SAFE program** and interviews over the course of three years starting as soon as IRB approval is obtained. We intend to complete the qualitative interviews and quantitative surveys in the first year. We intend to implement the SAFE program until approximately 120 participants have completed the program and data collection during year two and three. Recruitment will occur throughout the course of the study until the targeted number of participants is obtained. We will use block randomization, which will allow us to have continuous enrollment in the study.

Participation in the **SAFE program** is completed over the course of 2-4 weeks.

Participants will meet 2-3 times a week for approximately 60 minutes with either staff, a peer support specialist peer, or occupational therapy graduate students. The meetings will provide direct instruction and role play experiences covering the main concepts and proper use of preventable behaviors to protect against COVID-19 and other airborne diseases in the workplace.

Phase 2

Phase 2 will be completed over the course of one year following IRB approval. During the first two months, recruitment for the focus groups will take place. In months 2-4, focus groups will be conducted, and their feedback will be analyzed. Months 4-8 will involve revising the SAFE curriculum by adding lessons based on the focus group feedback. The final months will focus on recruitment and training.

Study Procedures and Data Analysis

Procedures.

To assess perceptions of peer-support interventions and use of preventative decision-making practices for individuals with ASD and or IDD in the workplace we will conduct in-depth qualitative interviews with individuals with ASD and or IDD working 10 hours or more a week (n=20 or until data saturation) who receive employment services or supports in order to: 1) understand the barriers and facilitators of implementing preventative decision-making practices for IADs and individuals with IDD in the workplace; 2) examine the perceptions and acceptability of peer support intervention strategies; and 3) develop a perceptual mapping survey instrument based on these findings.

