If the participant is assigned to the staff intervention support staff will be contacted with an email or phone call. Staff members will be required to complete human subjects training. Researchers will obtain informed consent for all participants. During the first contact made with participants, written information will be provided remotely using Zoom/FaceTime or in person to all participants explaining the following in simple terms: 1) the criteria for participation, 2) the purpose of the research and the procedures involved, 3) the subject's right to withdraw at any time without penalty of any sort, 4) potential benefits to the subject, 5) potential risks, 6) assurance of anonymity, and 7) terms of remuneration. All research staff will complete training about the informed consent process prior to consenting subjects. The information described above will be reviewed and any questions answered. Participants will be obtained signed or a printed signature box used for signature when electronic signatures are unable to be obtained for consent either in person or virtually.

We will collect data from young adults or transitional aged-youth with ASD or IDD to determine the efficacy and feasibility of the intervention. Recruitment occurs through the sites identified in the participant recruitment section of this proposal. Participants interested in the study will contact the primary investigator or research staff who will schedule an initial physical or virtual meeting at a place and time convenient for the participant to determine inclusion and obtain consent/assent. Participants are randomly assigned to either peer-support intervention, staff intervention or a control group. We will randomize in blocks of 12 (4 to each group) until we reach the targeted number of 120 or

SAFE Protocol

40 participants in each group. Pre-test and post-test measures will be administered by researcher staff prior to the start of the intervention (Pre-test) and at the end of the intervention 4 weeks (Post-test). Key stakeholders, including the participants and interventionists (occupational therapists and peer mediators), will complete qualitative interviews at the end of the intervention period for each participant. The information gathered will determine acceptability and feasibility of intervention. Participants will be asked to discuss their experiences during the intervention specific to their assigned intervention group.

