A member from the research team will then contact interested individuals to set up a convenient meeting time and place for the **SAFE** program training. These meetings will occur remotely or in a private location convenient to the participant. The **SAFE** program course training will occur in small group settings or individually. The course trainings will occur 2-3 times per week for between 45-60 minutes. An appropriate curriculum has been developed by Temple University Researchers and Occupational therapy students based on many qualitative interviews, research of proper education methods, and COVID-19 practices. The curriculum is based on a series of classes designed to create an understanding of best practices and behaviors to prevent the spread of COVID-19 in the workplace. The curriculum will be adapted to meet the needs of this project and study population. The course will provide instruction in the following areas: 1) COVID-19 and how it spreads 2) PPE and How to use it properly 3) Social Distancing 4) Community Participation 5) Employment 6) Self Efficacy.

Participants will complete the **SAFE** program sessions remotely or in person in a private, quiet and convenient setting.. Participants will be randomized into two treatment arms and a control group. The first treatment arm will receive the **SAFE** program implemented through a staff training model. The second group will receive the program using a peer support model. The control group will continue to receive their standard vocational rehabilitation supports.

Training of the **SAFE** program will occur remotely or person by staff who are trained within our research team or we will implement it in collaboration with staff or a peer specialist remotely as part of their current services. If it is in person it will be implemented at their vocational rehabilitation centers or places of employment. Research staff will be available to support the process after the training is complete.

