We will use a questionnaire to assess knowledge of actionable behaviors to prevent COVID-19, which reflect the core components of the *SAFE program* (social distancing, proper use of PPE, personal hygiene practices, and self-advocacy in the workplace). We will also administer measures to determine the degree of self-advocacy and self-efficacy in the work place reported by staff and self-reported by participants. We will determine how well a participant follows workplace procedures. Data will be collected either in person or virtually both at pre-test and post-test for all outcome measures. Finally, we will assess perceived anxiety.

Phase 2

Focus Group Participation

Recruited and consented participants will take part in focus groups consisting of 5-10 people. These focus groups will be held in convenient, private locations such as agency centers or conducted via Zoom to ensure both accessibility and privacy for all participants. During the focus groups, participants will be presented with a summarized and accessible version of the SAFE program. After reviewing the material, participants will share their experiences, priorities, and concerns, specifically focusing on any important priorities that they feel are missing from the current SAFE program curriculum. Research staff will facilitate these discussions. Each session will be recorded and transcribed using Zoom built in features to accurately capture the data. Focus groups will last no longer than two hours. Participants will be compensated \$30 for their participation.

Content Development for the SAFE Program

- Once the focus group analysis is completed, research staff will proceed with the creation of new content for the SAFE program. The team will draft educational materials that address the priorities identified during the focus groups. The draft content will undergo a rigorous review process through an advisory board involving subject matter experts, stakeholders, and individuals with lived experiences to ensure the content's accuracy and relevance. **Five to ten stakeholders will review the new content developed for the SAFE program. They will receive the newly developed content and provide feedback on its accessibility, clarity, and overall engagement. The content will be sent via email, and stakeholders will be asked to provide their feedback either through email or during a scheduled group Zoom meeting.**

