Based on the feedback received, research staff will make any necessary revisions to ensure the materials are both effective and accessible.

Once finalized, the new content will be integrated into the existing SAFE program materials. Research staff will adapt the content into various formats, including written guides, videos, and infographics, to meet the diverse learning needs of participants.

Pilot Testing for Service Providers

- Research staff will recruit 5-10 staff members from a large service provider organization to participate in pilot testing of the training materials. This pilot testing will occur over a 1-2 month period, during which staff will be trained on the new SAFE materials and additional content. The trainings will occur using Zoom meetings. The training sessions will be conducted either in groups or individually, depending on scheduling availability. Feedback will be collected from participants through surveys, interviews, or debriefing sessions to evaluate the effectiveness of the training. The training feedback will be audio recorded to ensure that we capture all important information you share. The audio recordings will be transcribed by the project team using Zoom's transcription feature. By signing the consent form, you are giving permission to be recorded.
 - Only people working on this project will have access to the recordings.
 - Information and transcripts will be stored securely in locked filing cabinets or on password-protected computers.

Based on this feedback, research staff will refine the training materials and curriculum, making necessary adjustments to improve clarity, accessibility, and applicability. These

SAFE Protocol

trainings will not be recorded. Feedback will only be collected using FIM surveys, AIM surveys and exit interview.

Once these refinements are complete, the finalized curriculum will be prepared for broader implementation within service-based organizations that support individuals with IDD. Participants will receive \$50 for the training. Participant will receive \$25 after the first training sessions and an additional \$25 after completion.

Data Analysis. Descriptive statistics including mean, median, standard deviation, skewness, frequencies, and percentages will be computed on demographic and measures as appropriate. We will complete ANOVAs to determine if there were significant changes in scores on outcome measures within and between groups. We will use SPSS to complete the analyses.

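### The planned ANOVAs are tied to neither the SAFE-effect question nor the peer-versus-staff question, and adjusting for the pre-test would usually be more precise at almost no cost

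*Combined protocol and SAP*

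**What the plan says.** The Data Analysis paragraph (section 9, Study Procedures and Data Analysis) plans descriptive statistics, the use of SPSS, and one inferential step: "We will complete ANOVAs to determine if there were significant changes in scores on outcome measures within and between groups". It gives no model form, contrast, covariate or alpha, and no other section supplies them. The perceptual survey items have a separate map-based comparison under Measures and are not part of this point.

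The Objectives (section 5) are more specific. One hypothesis reads "The program will have a larger effect on outcomes when provided using peer support compared to staff training". Question 1 asks whether SAFE participation will "increase perceived safety and well-being in the workplace for people with ASD and/or IDD", and question 2 asks the same of knowledge. Question 3 asks whether peer support gives a larger increase "than when implemented through staff training and supports".

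The Procedures text supplies what is needed to answer them. "Participants will be randomized into two treatment arms and a control group", with equal allocation: "We will randomize in blocks of 12 (4 to each group) until we reach the targeted number of 120", or 40 per group. On measurement, "Data will be collected either in person or virtually both at pre-test and post-test for all outcome measures".

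**The concern.** There are two questions and three arms, so at least two comparisons are needed: SAFE against control, and peer against staff. The analysis sentence names neither. If the analyst runs a three-group test and finds it significant, the plan does not say which question has been answered. The pairwise follow-up would then be chosen after the data are seen.

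The sentence also plans tests of change within groups. Any retest effect or time trend shared by all arms is part of a within-group change, so significance there does not by itself show a SAFE effect. Removing that shared change is what the randomised control arm is for.

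Finally, the pre-test score is collected anyway. Using it as a covariate is usually more precise than subtracting it, which matters in a trial expecting about 32 analysed participants per arm.

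**Working it through.** **Sample size.** Inclusion and Exclusion Criteria: 120 recruited with 20% attrition gives 120 × 0.80 = 96, which reproduces the stated figure; 96 / 3 = 32 per arm. Study Timelines instead enrols "until approximately 120 participants have completed the program and data collection", which gives 120 / 3 = 40 per arm. Recruitment Methods, Phase 1 names 120 with ASD plus 120 with IDD: 240 × 0.80 = 192, or 64 per arm. All three are carried below.

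**Assumptions not in the documents.** Two-sided alpha 0.05; true difference 0.5 post-test SD; independent participants; equal pre- and post-test SDs unless stated; pre/post correlation r shown over a range. Small-group delivery, which the Procedures allow, could make participants correlated and would lower the power figures.

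**1. What an omnibus test can separate.** For change scores the error variance is 2(1 − r). The noncentrality is n × Σ(arm mean − grand mean)² / [2(1 − r)], with n = 32 and 2 and 93 df.
- Both SAFE arms 0.5 SD above control, means (0, 0.5, 0.5): Σ = 0.1667.
- Only the peer arm 0.5 SD above, means (0, 0, 0.5): Σ = 0.1667.

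The noncentrality is the same in both cases: 5.33 at r = 0.5 and 8.89 at r = 0.7. Power is therefore also the same, 52% and 75%. A significant F cannot say which pattern is present. In the first pattern, a named SAFE-versus-control contrast (64 vs 32) on the same change scores has power 63% (r = 0.5) or 84% (r = 0.7).

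**2. ANCOVA against change score.** In units of post-test variance, the variance factor is 1 − r² for ANCOVA and 2(1 − r) for change scores. Their ratio is (1 + r)/2: 0.75, 0.85, 0.90 and 0.95 at r = 0.5, 0.7, 0.8 and 0.9. Noncentral-t power for peer versus staff uses noncentrality 0.5 / √(factor × 2/n). For example, at n = 32 and r = 0.5 it is 0.5 / √(0.75 × 0.0625) = 2.31 for ANCOVA and 0.5 / √(1 × 0.0625) = 2.00 for change scores.

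| Per arm | r = 0.5 | r = 0.7 | r = 0.8 | r = 0.9 |
|---|---|---|---|---|
| 32 | 62% vs 50% | 79% vs 72% | 91% vs 88% | no material gain |
| 40 | 72% vs 60% | 87% vs 81% | 96% vs 94% | no material gain |
| 64 | 90% vs 80% | 98% vs 95% | both above 99% | no material gain |

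(ANCOVA first, change score second.) Pooled SAFE versus control with 64 vs 32: 75% vs 63% at r = 0.5 and 89% vs 84% at r = 0.7.

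**3. Unequal SDs.** With k = pre-test SD / post-test SD, the ratio is (1 − r²) / [(k − r)² + 1 − r²]. It never exceeds 1 and equals 1 at k = r. At r = 0.7 and 32 per arm:
- k = 0.8: 0.51 / (0.01 + 0.51) = 0.98; power 79% vs 78%.
- k = 1.25: 0.51 / (0.3025 + 0.51) = 0.63; power 79% vs 59%.

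**4. Within-group tests (illustration only).** Suppose SAFE has no effect but every arm gains 0.2 to 0.4 SD on retest, a range assumed here. A paired t-test in one arm of 32 is then significant 20% to 59% of the time at r = 0.5, and 29% to 81% at r = 0.7.

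**The case against.** The sponsor can say that a change-score or group-by-time ANOVA is a valid analysis of a randomised trial and already uses the pre-test. That is right. A reader might infer that the planned ANOVA is biased or ignores baseline; the documents do not support that, and the precision part is about efficiency only.

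The sponsor can add that peer over staff is pre-specified, with a direction, in the Objectives. That is also right. It would be too strong to say the comparison is absent from the plan: what is missing is the link from the question to a test. The plan says ANOVAs in the plural and does not say that analysis stops at an omnibus F, but neither does it say what follows.

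On within-group tests, a reader might infer that the investigators intend to claim efficacy from them. The sentence permits that reading but does not state it, and it plans between-group tests as well.

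The study is also described as a pilot and a proof of concept. However, its title claims efficacy and its hypotheses are directional. Named contrasts with confidence intervals suit a pilot equally well.

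It is also tempting to conclude that the Workplace Health and Safety Assessment must be made the sole primary outcome because it comes first under the primary-outcomes heading. Several measures follow that heading, and this one does not cover the well-being part of question 1. The choice is the sponsor's and is not needed here.

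**Conclusion.** The point holds and should be acted on, though it does not invalidate the trial. Its firmest part needs no assumption about r: two stated questions, three arms, and no test assigned to either question. The equality of omnibus power under the two patterns is exact for equal arms and equal 0.5 SD steps.

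The precision part is firm in direction for large samples but uncertain in size. With equal SDs the gain for peer versus staff at 32 per arm is about 12 percentage points at r = 0.5, 7 at r = 0.7 and 3 at r = 0.8, and nothing material at r = 0.9. With unequal SDs at r = 0.7 it ranges from about 1 point (k = 0.8) to 20 points (k = 1.25). The 0.5 SD difference, the alpha and the independence of participants are also assumptions. The conflict between the recruitment totals is a separate point: it moves the powers but not the variance ratio or the missing link.

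**What to change.** Replace the ANOVA sentence with text such as:

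*For each scale score recorded for randomised participants at both pre-test and post-test, the post-test score will be analysed by ANCOVA with randomised arm and the corresponding pre-test score, with participants analysed in the arm assigned. Two pre-specified contrasts, SAFE (both arms) versus control and peer versus staff, will be reported with 95% confidence intervals. Within-group changes are descriptive only. AIM and FIM, collected only at post-test, will be summarised descriptively.*

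The restriction to measures taken at both times is needed because, under Measures (Feasibility Data), AIM and FIM are completed only at post-test and FIM comes from the interventionists. They have no baseline to adjust for.

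The cost is one covariate degree of freedom and a different SPSS procedure, with no new data or visits. Testing both contrasts at 0.05 without adjustment gives a chance of about 1 − 0.95² = 0.0975, or roughly 10%, of at least one false positive per outcome. Whether and how to control that is the sponsor's choice, and any control costs some power. For example, at alpha 0.025 and 32 per arm, ANCOVA power for peer versus staff falls to 51% (r = 0.5) or 69% (r = 0.7).

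### The plan does not say that efficacy rests on the between-arm comparison, so a within-arm pre-post p-value could confirm SAFE without using the randomised control arm

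*Combined protocol and SAP*

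**What the plan says.** The quantitative analysis of the randomised comparison is one sentence in section 9, Data Analysis: "We will complete ANOVAs to determine if there were significant changes in scores on outcome measures within and between groups". Descriptive statistics and the software are also given. No group-by-time term, SAFE-versus-control contrast, baseline adjustment or significance level is named, and no result is designated as deciding efficacy.

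Section 5 states one hypothesis as a gain after the programme: "Individuals with IDD will demonstrate increased knowledge and safe behaviors after completing the" SAFE program. Research question 1 asks whether participation will "increase perceived safety and well-being in the workplace for people with ASD and/or IDD". Question 2 asks in the same way about knowledge. Neither names a comparator. One hypothesis is comparative: "The program will have a larger effect on outcomes when provided using peer support compared to staff training". Question 3 repeats that comparison.

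The design supports a controlled comparison. In section 9, Procedures, "Participants are randomly assigned to either peer-support intervention, staff intervention or a control group", and "The control group will continue to receive their standard vocational rehabilitation supports". Outcomes are measured at pre-test and again at post-test, at 4 weeks.

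**The concern.** Randomisation protects the comparison between arms. It does not protect the change inside one arm. Scores can rise over 4 weeks because participants have met the questions before, or because something in their workplaces or the wider setting changed over the period. A within-arm test cannot separate such a rise from an effect of SAFE.

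The test sentence includes within-group significance, and several efficacy statements are worded so that a pre-post gain would answer them. Put together, a team could follow the document faithfully and report a SAFE effect when SAFE does nothing, with the control data playing no part. The credibility of the claim that SAFE works is at stake. Whether peer delivery beats staff delivery is less exposed, because that question is already comparative.

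**Working it through.** **Inputs from the documents.** There are three arms: "We will randomize in blocks of 12 (4 to each group) until we reach the targeted number of 120 or" "40 participants in each group". The Inclusion and Exclusion Criteria give 120 recruited, 20% attrition and 96 in the final sample. This reproduces: 120 × 0.8 = 96, or 96 / 3 = 32 per arm if losses are equal. (Recruitment Methods attaches the same 96 to 120 with ASD plus 120 with IDD, but 240 × 0.8 = 192. I use the version that reproduces and that matches 40 per arm.)

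**Inputs assumed.** The documents give no SD, pre-post correlation, retest gain or significance level. I assume two-sided 0.05, no SAFE effect, the same true gain g (in SDs of the score) in every arm, and pre-post correlation r.

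**Formulas.** A within-arm ANOVA with two time points is equivalent to a paired t-test.
- SD of change = √(2(1 − r))
- Noncentrality = g / SD of change × √32
- P = probability that a noncentral t with 31 df falls beyond ±2.04
- At least one of the two SAFE arms = 1 − (1 − P)², since the arms are independent

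**Results, 32 per arm.**

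| g | r | SD of change | Noncentrality | One SAFE arm significant | At least one of two |
|---|---|---|---|---|---|
| 0.1 | 0.5 | 1.000 | 0.57 | 9% | 16% |
| 0.1 | 0.8 | 0.632 | 0.89 | 14% | 26% |
| 0.2 | 0.5 | 1.000 | 1.13 | 20% | 35% |
| 0.2 | 0.8 | 0.632 | 1.79 | 41% | 65% |
| 0.3 | 0.6 | 0.894 | 1.90 | 45% | 70% |

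Worked for the last row: √(2 × 0.4) = 0.894; 0.3 / 0.894 × √32 = 1.90; P = 0.452; 1 − 0.548² = 0.70.

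**Reference values.** With no shared gain, each arm is significant 5% of the time and at least one of two 1 − 0.95² = 9.75%. The right-hand column should be read against about 10%. The 9% in the first row counts significant change in either direction; counting gains only, it is 7.9%.

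**Between-arm test on the same data.** A gain common to all arms cancels in the difference between arms. In 20,000 simulated trials with 32 per arm, a one-way ANOVA on change scores was significant 4.6%, 5.3% and 5.0% of the time. The common gains were 0.2, 0.35 and 0.5, here in SDs of the change score.

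**Sensitivity to n.** With all 40 per arm analysed, gains of 0.1 to 0.2 SD and r of 0.5 to 0.8 give 9% to 50% per arm and 18% to 75% for at least one of two. More participants make the within-arm problem worse.

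**The case against.** The best defence is that the sentence also plans between-group tests, and that within and between are the usual names for the two factors of a mixed pre-post ANOVA. On that reading the controlled comparison is already there. This stands in part: a valid between-arm test is not absent, and the sentence ranks neither result above the other. But the plan names no group-by-time term, and even a mixed ANOVA yields a main effect of time that a shared gain would make significant.

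Three stronger readings are tempting, and the documents do not support them.
- A reader might infer that within-arm p-values are given equal weight or are intended as the efficacy evidence. No passage says so; the fault is silence about which result decides.
- A reader might infer that peer superiority will be claimed because one arm is significant and the other is not. That aim is worded as a direct comparison in both the hypothesis and question 3, and nothing proposes comparing verdicts across arms.
- A reader might infer that a between-arm test would also remove expectancy. It would not: control receives only standard supports, and no assessor blinding is described.

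Two further points are fair. The abstract frames the work partly as feasibility and proof of concept, although the title and hypotheses speak of efficacy. And 8 of the 20 items in the Workplace Health and Safety Assessment are observed at work, so repeated exposure to the questions bears directly only on the 12 that the participant answers.

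**Conclusion.** The concern holds as a gap in the decision rule. The plan includes a within-group significance test and words a hypothesis and two research questions without a comparator. It never states that efficacy depends on the comparison between arms.

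The size of the risk depends wholly on the assumed shared gain. At 0.1 SD with r = 0.5 the excess is modest: 9% per arm against 5%. At 0.2 SD with r = 0.8, or 0.3 SD with r = 0.6, it is over 40% per arm. These figures assume equal attrition across arms, independent participants and roughly normal change scores. The direction does not depend on the particular values: any shared gain above zero inflates the within-arm test and leaves the between-arm test at its nominal level. The matter should be settled before analysis, but the design itself needs no repair.

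**What to change.** In section 9, Data Analysis, state that efficacy will be concluded only from the between-arm comparison of change: the group-by-time test, with each SAFE arm against control and peer against staff. State that within-arm change is descriptive, reported as a mean with 95% CI, and supports no efficacy claim.

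In section 5, reword the hypothesis and research questions 1 and 2 as greater increases than in the control group.

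Acknowledge that this removes shared retest and calendar-time gains but leaves expectancy, given a control on standard supports and no described blinding of assessors.

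The cost is a few sentences, with no new data and no extra participants. The sponsor gives up within-arm p-values as evidence of efficacy.
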